### **7.9.2.1. Primary Pharmacodynamic Analysis**

#### **7.9.2.1.1. Energy Intake via Ad-libitum Food Intake Test**

The primary endpoint in this study is the change from baseline to Week 3 in energy intake (kcal) as assessed by an ad-libitum food-intake test at lunch in a clinical setting for the comparison of 5-mg tirzepatide versus placebo.

For clinical settings, the amount of grams of fat (saturated and unsaturated), carbohydrates, and protein consumed will be documented in the eCRF. These calories will be represented in kcal format using the following conversion: 1 gram of carbohydrate or protein = 4 kcal, 1 gram of saturated fat or unsaturated fat = 9 kcal. The energy intake will be calculated as the total calories (kcal) and recorded in an eCRF as well. The percentage of fat, carbohydrate, and protein in total energy may be derived:

- food intake
  - g (that is, the amount of grams of food consumed)
- fat (saturated and unsaturated)
  - g and kcal

- percent of energy (that is, fat [kcal]/energy intake [kcal])
- carbohydrate
  - g and kcal
  - percent of energy (that is, carbohydrate [kcal]/energy intake [kcal]), and
- protein
  - g and kcal
  - percent of energy (that is, protein [kcal]/energy intake [kcal]).

The primary endpoint will be analyzed using an analysis of covariance to compare the effect of tirzepatide versus placebo at Week 3 on lunch energy intake (kcal) with treatment as fixed effect, baseline BMI stratum, and baseline energy (kcal) intake as covariates in the model using the PD analysis set.

Inferential statistics will include LSMs (Standard error) of energy (kcal) intake by treatment and the treatment difference of tirzepatide versus placebo in LS Mean difference with 95% CI, and the p value for treatment comparison will be displayed.

### **7.9.2.2. Secondary Pharmacodynamic Analyses**

Secondary PD measures (that is, BOLD fMRI activation; VAS; and the FCI, FCQ-S, TFEQ, and Power of Food Scale questionnaires [see Section 7.10.1 for details]) are scheduled to be measured twice postbaseline at Week 3 and Week 6.

The PD measurements will be analyzed using a MMRM method to compare the effect of tirzepatide versus placebo at Week 3. The response variable is change from baseline in the PD measurement (that is, postbaseline - baseline), where postbaseline measurement is collected at Week 3 and Week 6. The model will include treatment, baseline BMI stratum, week, and treatment-by-week interaction as fixed effects and baseline PD measurement as a covariate; scanner ID will be included as a covariate for modelling the function MRI parameters as well. An unstructured covariance structure will be used to model the within-subject variabilities if deemed appropriate. The restricted-maximum-likelihood approach will be used to obtain model parameter estimates.

For both secondary and exploratory PD parameters, a single model for each parameter will be constructed. The inferential results will be displayed into section for secondary endpoints and section for exploratory endpoints, separately.

For secondary endpoints, inferential statistics will include LSMs (Standard error) of each treatment, the treatment difference with 95% CI at Week 3, along with the p value for comparison.

#### **7.9.2.2.1. *Central Reward and Appetite Circuits in the Fasting State using BOLD fMRI***

Secondary PD measures to assess the effect of 5-mg tirzepatide versus placebo at Week 3 on parameters of central reward and appetite circuits during fasting and postprandial states using BOLD fMRI are

- change from baseline in mean difference to Week 3 in BOLD fMRI activation to images of highly palatable food (versus nonfood objects) during fasting states in 5 brain reward and appetite areas (insula, medial frontal gyrus, superior temporal gyrus, precentral gyrus, and cingulate gyrus).

The 5 principal brain reward and appetite ROI to be examined and recorded will be

- insula
- medial frontal gyrus
- superior temporal gyrus
- precentral gyrus, and
- cingulate gyrus.

Four additional exploratory brain reward and appetite ROI to be examined and recorded will be

- hippocampus
- putamen
- orbitofrontal cortex, and
- ventral striatum.

Mean differences in BOLD signal between views of highly palatable food (high-fat, high-sugar and high-fat, high-carbohydrate) versus nonfood objects (for example, office supplies and furniture) will be calculated within 5 principal food-reward and appetite-related ROI and 4 exploratory food-reward and appetite-related ROI.

These validated contrast values (that is, mean difference in BOLD signal) (continuous) will be provided by image data processing vendor (Clario) to statisticians/programmers for analyses. Change from baseline in BOLD contrast values at Week3 and at Week6 will be summarized by treatment.

Additional analyses using other functional contrasts (for example, highly palatable foods versus not highly palatable foods [low-fat, low-carbohydrate, high-protein] and not highly palatable foods versus nonfood objects) may be conducted at the 5 principal food-reward and appetite-related ROI and 4 exploratory food-reward and appetite-related ROI if deemed necessary.

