#### **Measures of Central Reward and Appetite Circuits**

• BOLD fMRI: Mean percent BOLD signal differences between views of highly palatable food (HF-HS and HF-HCCHO) versus non-food objects (e.g. office supplies, furniture) will be calculated within 5 principal food reward-related regions of interest; distinct locations within the insula, medial frontal gyrus, superior temporal gyrus, precentral gyrus, and cingulate gyrus. Additional analysis will examine the BOLD signal differences in 4 exploratory food reward-related regions of interest; the hippocampus, putamen, orbitofrontal cortex, and ventral striatum.

Additional analyses using other functional contrasts (e.g., Highly Palatable foods versus Not Highly Palatable Foods, not highly palatable foods versus nonfood objects) may be conducted as necessary. Other PD measures and exploratory measures will be described in the SAP.

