# 5.2 Magnetic Resonance Imaging

Functional neuroimaging, in the forms of BOLD fMRI will be used to assess brain response patterns to food and non-food images. The MRI scanning will occur on different scanners such as a 3T General Electric Discovery 750W with 32-channel head coil, a 3T General Electric Discovery 750 with 32-channel head coil, a 3T Siemens Prisma with a 64-channel head coil, or a 3T Philips Achieva with a 32-channel head coil. Functional neuroimaging session will be conducted after participants fast overnight for at least 8 hours (ten Kulve et al. 2016).

Subjects will be required to complete the food image task during the BOLD fMRI scan. The food image task was developed using images from the Food-pic database (Blechert et al. 2014). Briefly, 90 food images across sweet and savory tastes, high- and low-energy density, and varied macronutrient composition, were included along with 15 images of non-food objects (e.g. everyday household objects). This results in 105 images in total. Macronutrient categories (Geiselman et al. 1998) were made by categorizing each food as:

- low versus high fat (LF vs HF, <30% vs >30%)
- low versus high sugar (LS vs. HS, <30% vs. >30%)
- low versus high carbohydrate (LCCHO vs HCCHO, <30% vs >30%)
- low versus high protein (LP vs HP, <13% vs >13%)

This resulted in 6 food categories with 15 photos in each:

- 1. HF/HS
- 2. HF/HCCHO
- 3. HF/LCCHO/HP
- 4. HS/LF
- LF/HCCHO
- 6. LF/LCCHO/HP

Each  $600 \times 450$  color photo shows 1 food on a white background.

Among the 6 food categories, HF-HS and HF-HCCHO will be called highly palatable (PAL) food and LF-LCCHO-HP will be called not highly palatable (NPAL) food.

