In each trial of the task, 1 food photo is displayed for 5 seconds followed by 0.5 seconds of a fixation crosshair. Next, the same image scaled to 80% of the original size is shown with the words "How much do you want to eat this?" for 2.5 seconds. A slider bar with "Not at all" and "Want very much" on the left and right ends appears. The subject moves a joystick to select a slider bar position and clicks a joystick button to respond. A fixation crosshair displays for a minimum of 1.5 seconds before the next trial. There are 15 trials (i.e. 15 photos) per block and 14 inter-trial intervals per block: an average of 150 s/block. This is followed by a 30 s interblock interval before the next block. total of 7 blocks and 6 inter-block intervals: 20.5 minutes of recorded data. Prior to the beginning of the task, subjects will be given time to practice the task in the scanner. Additionally, a high-resolution structural scan will be acquired. The total duration of each MRI session will be around 40 minutes.

For the purposes of evaluating inter-scanner variability to ensure that the fMRI data from all sites can be analyzed collectively at the end of the study, subjects will be required to complete a bilateral hand squeeze motor task during the BOLD fMRI scan, consisting of 4 blocks after the food image task. Each block will consist of 30 seconds of bilateral hand squeezing followed by 30 seconds of rest (around 3 minutes total run time).

To model respiratory and cardiac effects on the BOLD signals, participants will be fitted with a lap belt and pulse oximeter. The respiratory cycle signal and cardiac cycle signal will be regressed out of all time series data.

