## 4. Revision History

Statistical analysis plan version 1 was approved on 25 June 2020 prior to the first patient visit.

Statistical analysis plan version 2 was approved on 09 June 2022 prior to database lock.

The major revisions in version 2 include

- modified study procedure and schedule of activities based on Protocol (f)
- updated sample size to approximately 111 subjects (37 subjects per treatment arm) planned to be randomly assigned, and
- reorganized and rephrased the PD analyses section.

Statistical analysis plan version 3 was approved prior to database lock.

Major revisions in version 3 include

- Change of specification of the BOLD fMRI analysis variables. Contrasts between conditions are defined as the mean difference as opposed to mean percent difference. This is because dividing by the non-food contrast was causing falsely large numbers in scans where the subject had low activation to non-food objects (that is, division by number close to 0).

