## 9. Change from the Protocol-Specified Statistical Analyses

For BOLD fMRI, the *percent* BOLD signal differences between views of highly palatable food (HF-HS and HF-HCCHO) versus non-food objects (for example, office supplies, furniture) was defined as the analysis variable. In data review in a blinded manner, quite a few extreme outliers were found, as there were a significant number of observations close to zero for non-food objects (the denominator in the percent change calculation). Therefore, the percent BOLD contrast was replaced with *absolute* BOLD contrast as the analysis variable.

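### Does the absolute BOLD contrast in SAP version 3, which has no stated unit or scaling, undermine pooling across scanners?

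*SAP*

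**What the plan says.** Protocol 10.3.3.1 defined the fMRI variable as "Mean percent BOLD signal differences between views of highly palatable food (HF-HS and HF-HCCHO) versus non-food objects". SAP version 3 changed this. SAP Section 4 records that "Contrasts between conditions are defined as the mean difference as opposed to mean percent difference", and SAP Section 9 explains that blinded data review found extreme outliers, "as there were a significant number of observations close to zero for non-food objects (the denominator in the percent change calculation". SAP 7.9.2.2.1 now specifies "Mean differences in BOLD signal between views of highly palatable food (high-fat, high-sugar and high-fat, high-carbohydrate) versus nonfood objects" and says of the source: "These validated contrast values (that is, mean difference in BOLD signal) (continuous) will be provided by image data processing vendor".

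Protocol Appendix 5, Section 5.2 states: "The MRI scanning will occur on different scanners such as a 3T General Electric Discovery 750W with 32-channel head coil". It goes on to name further models from other manufacturers, with 32- or 64-channel coils. Preprocessing is assigned to an external imaging provider.

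There are two provisions for scanner differences:

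- **In the model.** SAP 7.9.2.2 states: "scanner ID will be included as a covariate for modelling the function MRI parameters as well".
- **In data collection.** Protocol Appendix 5 adds a bilateral hand-squeeze task for the purpose of "evaluating inter-scanner variability to ensure that the fMRI data from all sites can be analyzed collectively at the end of the study", and says that its contrast will be computed. The SAP does not mention this task.

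**The concern.** The percent ratio was the only scale normalisation that either document states, and version 3 removed it without putting another in its place. If one scanner delivers signal at twice the scale of another, an absolute difference is also twice as large on that scanner. Change from baseline does not remove the factor, and a scanner intercept shifts the mean without touching the slope.

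The pooled treatment difference would then be a gain-weighted average with no fixed unit, dominated by the highest-gain scanner, with a wider interval than necessary. This variable carries the five-region secondary endpoint, the nine-region exploratory comparisons, and the role of liraglutide as neuroimaging positive control. The hand-squeeze data, collected to support pooling, have no stated use in the SAP.

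**Working it through.** **What the documents give.** There is no sample size or power statement for fMRI. The only sizing is for energy intake (Protocol 10.1): a difference of 212 kcal and an SD of 289 kcal, so 212/289 = 0.734 SD. A two-sample t-test at two-sided 0.05 needs 30.16, hence 31 per arm, and its power at 31 is 81.1%. Then 31/0.85 = 36.5, hence 37 per arm and 3 × 37 = 111. The plan's figures reproduce. The effect of 0.734 SD is borrowed below purely as a yardstick.

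**Effect of a gain factor.** Let scanner gain *g* multiply the palatable-food value *P* and the non-food value *N*.

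- Old variable: (gP − gN)/(gN) = (P − N)/N, so *g* cancels.
- New variable: gP − gN = g(P − N), so *g* stays, and it stays in the change from baseline.

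**Cost if values are unscaled.** Let scanner shares be *w* and gains *g*, with an additive scanner term. The expected treatment estimate is (Σwg) times the common-scale effect, and the residual variance is proportional to Σwg². Hence

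relative efficiency = (Σwg)² / Σwg², and CI width factor = 1/√(relative efficiency).

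Worked case, four equal scanners with gains 1, 1, 1.5, 2: Σwg = 5.5/4 = 1.375 and Σwg² = 8.25/4 = 2.0625. Efficiency = 1.8906/2.0625 = 0.917, and the CI factor is 1.044.

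The power columns come from simulation: 6,000 trials per case, 31 per arm, four equally likely scanners, single-visit ANCOVA with treatment, baseline and scanner. All gains are assumptions.

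| Gains | Efficiency | CI factor | Power, unscaled | Power, rescaled | Mean estimate, unscaled |
|---|---|---|---|---|---|
| 1, 1, 1, 1 | 1.000 | 1.000 | 77.7% | 77.8% | −0.73 |
| 1, 1, 1.25, 1.5 | 0.970 | 1.015 | 76.9% | 78.3% | −0.87 |
| 1, 1, 1.5, 2 | 0.917 | 1.044 | 73.7% | 78.3% | −1.00 |
| 1, 1, 2, 3 | 0.817 | 1.107 | 70.8% | 78.5% | −1.28 |
| 1, 1, 3, 5 | 0.694 | 1.200 | 63.1% | 78.8% | −1.82 |

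The mean estimates follow Σwg × 0.734 (for example 1.375 × 0.734 = 1.01). Simulated type I error with unscaled values was 4.6% to 5.3%, which is 5% within simulation error: with no treatment effect, a gain multiplies noise alike in both arms.

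**Which row applies?** The documents do not say, but they contain a clue. Raw mean signal in a brain region would not sit near zero. SAP Section 9 reports that the non-food values often did, and SAP Section 4 describes the troublesome scans as ones with little response to the non-food images. So *P* and *N* look like baseline-referenced activation estimates. That excludes the crudest reading of absolute as raw intensity. It does not prove a common scale, because model estimates in arbitrary units can also lie near zero.

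**Was the old ratio a real safeguard?** It cancelled *g*, but as *N* approaches 0 the ratio (P − N)/N grows without bound. A variable dominated by outliers of that kind is no better basis for pooling than a difference with moderate scale variation.

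**The case for a change.** The strongest case for acting is that a reader cannot tell from either document what unit the reported least squares means and intervals will be in. The change made to cure near-zero denominators also removed the only stated normalisation, and SAP Sections 4 and 9 do not discuss that side effect. The protocol saw the pooling problem clearly enough to add a motor task for it, yet the SAP gives no analysis, criterion or fallback for that task. A vendor confirmation, a sentence and a table by scanner would cost little.

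The textual part stands: unit and scaling are unstated, scanner ID is the only scanner term in the SAP, and an additive term cannot correct a multiplicative difference. The inference to harm does not stand:

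- Silence in the SAP about processing that the protocol assigns to a specialist provider does not show that the values are unscaled.
- Pooling does not rest on the covariate alone. The hand-squeeze contrast is computed under the protocol whether or not the SAP repeats it.
- The larger power losses come from gain ranges with no source in the documents, and are measured against a power that the trial never claimed for fMRI.
- Redefining the contrast as a percentage of run-mean signal would be a third definition after data review. It would gain nothing if the values are already scaled, and would not equalise BOLD sensitivity between scanners and coils if they are not.

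**Conclusion.** No change follows. The switch from a percent to an absolute contrast was made for a sound reason, in blinded review, and is declared in SAP Sections 4 and 9. What remains is a gap in description. The vendor that supplies the values can state their unit and scaling, and the analysts can label the output accordingly and read the hand-squeeze contrast by scanner, without altering the planned analysis.

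The loss is nil if the values are on a common scale. If they are not, it depends on gains and scanner shares that the documents do not give: 1.5% on interval width at an assumed 1.5-fold range, about 4% at 2-fold, and more only under wider ranges that nothing in the documents supports. These figures assume equal scanner use, variability that scales exactly with gain, and one post-baseline visit where the SAP has a repeated-measures model. Type I error stays near 5%, the affected results are secondary or exploratory, and the primary endpoint is untouched. The documents do not show that following the plan as written gives a wrong or worse answer.

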#### **7.9.2.2. *Behavioral Appetite Assessments***

Secondary PD measures to assess the effect of 5-mg tirzepatide versus placebo at Week 3 on parameters of behavioral appetite assessments are

- change from baseline to Week 3
  - in fasting and postprandial appetite VAS (laboratory-based), and
  - fasting FCI, FCQ-S, TFEQ, and Power of Food Scale questionnaires.

The parameters will be summarized for each at lead-in, Week 3, and Week 6, and the change from baseline at Week 3 and Week 6 will be also summarized. The comparison of secondary objective parameters will be analyzed using an MMRM model respectively for each parameter.

- Response variable - Change from baseline in a secondary PD parameter.

- Independent variables - Treatment, time, and treatment-by-time interaction as fixed effects; baseline value in secondary parameter as a covariate; and patient as a random effect.

Inferential statistics include LSMs and standard error of each of the secondary objective parameters for tirzepatide and placebo, and the estimated treatment difference (tirzepatide versus placebo) at Week 3, corresponding 2-sided 95% CI, and associated p-values.

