### 3. List of Abbreviations

Term	Definition
ADA	anti-drug antibody
BIS	Barratt Impulsiveness Scale
BMI	body mass index
BOLD fMRI	blood-oxygenation-level-dependent functional magnetic resonance imaging
AE	adverse event
AESI	adverse event of special interest
CI	confidence interval
COVID-19	coronavirus disease 2019
ECG	electrocardiogram
FCI	Food Craving Inventory
FCQ-S	Food Craving Questionnaire-State
GIP	glucose-dependent insulinotropic polypeptide
GLP-1	glucagon-like peptide 1
IPD	important protocol deviation
Lilly	Eli Lilly and Company
LSM	least squares means
MedDRA	Medical Dictionary for Regulatory Activities
MMRM	mixed effects model of repeated measures
MRI	magnetic resonance imaging
PD	pharmacodynamic(s)
PK	pharmacokinetic(s)
PT	Preferred Term
PYY	peptide YY
QD	once daily
QL	quantification limit

Term	Definition
QW	once weekly
ROI	region of interest
SAE	serious adverse event
SAP	statistical analysis plan
SOC	System Organ Class
TE-ADA(+)	treatment-emergent anti-drug antibody (positive)
TEAE	treatment-emergent adverse event
TFEQ	Three-Factor Eating Questionnaire
VAS	visual analog scale

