**Table GPHH.5.1. Objectives and Endpoints**

Objectives	Endpoints

Primary
 
To compare the effect of 5-mg tirzepatide versus placebo, at Week 3, on energy intake in a clinical setting
	
 
Change from baseline in energy intake (kcal) as assessed by ad-libitum food-intake test
 

Secondary
 
To compare the effect of 5-mg tirzepatide versus placebo, at Week 3 on
 
 
Parameters of central reward and appetite circuits in the fasting states using BOLD fMRI
 
Parameters of behavioral appetite assessments
 
	
 
Change from baseline in BOLD fMRI activation to images of highly palatable food (high fat-high sugar and high fat-high carbohydrate) during the fasting state in the brain reward areas (insula, medial frontal gyrus, superior temporal gyrus, precentral gyrus, and cingulate gyrus)
 
Change from baseline in fasting and postprandial appetite VAS, and fasting FCI, FCQ-S, Eating Inventory, and Power of Food Scale questionnaires
 

Exploratory
 
To compare the effect of 5- or 10-mg tirzepatide versus placebo at Week 3 and/or Week 6 on
 
 
Parameters of central reward and appetite circuits in the fasting state using BOLD fMRI (Week 6/10 mg)
 
Parameters of behavioral appetite assessments (Week 6/10 mg)
 
Energy intake in a clinical setting (Week 6/10 mg)
 
	
 
Change from baseline in BOLD fMRI activation to images of highly palatable food (high fat-high sugar and high fat-high carbohydrate) versus non-food objects during the fasting state in the brain reward areas (insula, medial frontal gyrus, superior temporal gyrus, precentral gyrus, cingulate gyrus)
 
Change from baseline in fasting and postprandial appetite VAS, and fasting FCI, FCQ-S, Eating Inventory, and Power of Food Scale questionnaires
 
Change from baseline in energy intake (kcal) as assessed by ad-libitum food-intake test
 

Objectives	Endpoints

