### **7.10.1. Adverse Events**

Adverse events for the safety population will be listed, which will include the MedDRA PT.

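### The SAP gives two different MMRMs for the same behavioral secondary endpoints, and only one of them contains the BMI randomization stratum

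*SAP*

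**What the plan says.** SAP Section 7.9.2.2 (Secondary Pharmacodynamic Analyses) names BOLD fMRI, VAS, FCI, FCQ-S, TFEQ (the Eating Inventory) and the Power of Food Scale, and specifies an MMRM for them: "The model will include treatment, baseline BMI stratum, week, and treatment-by-week interaction as fixed effects and baseline PD measurement as a covariate". It uses REML and adds scanner ID for the fMRI parameters only. On covariance it says: "An unstructured covariance structure will be used to model the within-subject variabilities if deemed appropriate". It then commits to one model: "For both secondary and exploratory PD parameters, a single model for each parameter will be constructed".

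The Behavioral Appetite Assessments section (7.9.2.2.2 in the SAP's table of contents) names the same VAS and questionnaires and gives its own list of independent variables: "Treatment, time, and treatment-by-time interaction as fixed effects; baseline value in secondary parameter as a covariate; and patient as a random effect". This list has no BMI stratum, no residual covariance structure and no reference back to the parent section.

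The subsections for appetite VAS, FCI, FCQ-S, TFEQ, Power of Food Scale and BIS each refer for their MMRM to the start of the section, without a number. Protocol Section 10.3.3.2 leaves the secondary analyses to the SAP. SAP Section 9 records only the change of BOLD contrast.

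**The concern.** The two descriptions cannot both be the single model that Section 7.9.2.2 promises. BMI stratum is the stratification factor of the randomization (SAP Section 6.1) and is in the primary ANCOVA (SAP Section 7.9.2.1.1). A programmer who codes the behavioral list as written leaves it out. If BMI is prognostic for these scores, the reported standard error is then too large and the test is conservative.

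The patient random effect is a second difference. With only two post-baseline visits, a random intercept on top of an unstructured residual matrix is not identifiable. On its own, with equal residual variances, it implies compound symmetry, which pools the Week 3 variance (tirzepatide 5 mg) with the Week 6 variance (10 mg). The Week 3 standard error is then too small if Week 6 is less variable and too large if it is more variable.

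The affected results are the Week 3 treatment differences, confidence intervals and p-values for the behavioral secondary endpoints. Leaving the choice open also allows it to be made after results are seen.

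**Working it through.** **Side-by-side comparison**

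| Element | Section 7.9.2.2 | Behavioral Appetite Assessments |
|---|---|---|
| Treatment, visit, interaction | yes | yes |
| Baseline value | yes | yes |
| BMI stratum | yes | no |
| Patient random effect | no | yes |
| Residual covariance | unstructured, with a qualifier | not stated |
| REML | stated | not stated |

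**Does anything in the documents settle it?** No. Both sections open with a model, so a pointer to the start of the section fits either. The one numbered cross-reference for these measures, "see Section 7.10.1 for details", leads to a section that begins: "Adverse events for the safety population will be listed, which will include the MedDRA PT". It gives no help.

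**Analyses affected.** The secondary row of Table GPHH.5.1 names the instruments: "Change from baseline in fasting and postprandial appetite VAS, and fasting FCI, FCQ-S, Eating Inventory, and Power of Food Scale questionnaires". The subsections give the scores to be modeled: 2 laboratory VAS overall scores (fasting, postprandial) + 1 FCI + 1 FCQ-S + 3 TFEQ factors + 4 Power of Food scores = 11. Adding the retrospective VAS overall score gives 12. Adding the BIS scores (6 + 3 + 1 = 10), which the BIS subsection calls secondary but Table GPHH.5.1 lists as exploratory, gives 22.

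**The plan's own figure.** The only powered comparison is the primary one. With SD 289 kcal, difference 212 kcal, 31 completers per arm and two-sided 0.05, the t-test power is 81.1%, and 31/0.85 = 36.5, or 37 per arm. This reproduces, and the present point does not change it.

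**Size of the discrepancy.** No variances are given for the behavioral scores, so the inputs below are assumed. Let R² be the share of the variance left after baseline adjustment that BMI stratum explains, and r = SD at Week 6 / SD at Week 3. With complete data and near-balanced strata, the Week 3 SE from the behavioral list, relative to Section 7.9.2.2, is multiplied by

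k = 1/√(1 − R²) for the BMI omission (r = 1), or k = √((1 + r²)/2) for pooled variances (R² = 0).

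Type I error = 2·P(t₈₈ > 1.987k). For a comparison with 80% power under Section 7.9.2.2, power = P(Z > 1.987k − 2.83). The 88 degrees of freedom approximate what 93 completers leave: 87 with the stratum, 89 without.

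*BMI omission only (r = 1)*

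| R² | k | Type I error | Power |
|---|---|---|---|
| 0 | 1.000 | 5.0% | 80.0% |
| 0.02 | 1.010 | 4.8% | 79.5% |
| 0.05 | 1.026 | 4.5% | 78.6% |
| 0.10 | 1.054 | 3.9% | 76.9% |

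*Random intercept with equal residual variance only (R² = 0)*

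| r | k | Type I error |
|---|---|---|
| 0.8 | 0.906 | 7.5% |
| 1.0 | 1.000 | 5.0% |
| 1.25 | 1.132 | 2.7% |
| 1.5 | 1.275 | 1.3% |

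**Simulation check.** Both models were fitted to 93 completers in three arms, with baseline in both and an assumed within-subject correlation of 0.6.

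- R² = 0, r = 0.8, 1.25 and 1.5 (4,000 replicates each): median SE ratios 0.906, 1.130 and 1.273; type I error 7.4%, 2.4% and 1.4% under the behavioral list, against 4.8%, 4.5% and 4.9% under Section 7.9.2.2.
- r = 1, R² = 0, 0.02 and 0.10 (16,000 replicates each): SE ratios 0.999, 1.010 and 1.054; type I error 4.9%, 4.6% and 3.8%, against 4.9%, 4.9% and 5.0%.

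These agree with the closed form.

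**The case against.** The strongest reply is that Section 7.9.2.2 plainly governs. It is the parent section, names every instrument, promises one model per parameter and is the only place where an fMRI model is given. On that view the behavioral list is an abbreviated restatement. The random effect may be loose wording for the repeated subject factor, since the SAP's abbreviation list expands MMRM as "mixed effects model of repeated measures". The 7.5% type I error needs both the random-intercept reading and a less variable Week 6, and the documents support neither. Section 7.9.2.2 does not itself fix the unstructured matrix unconditionally. What remains is the BMI omission, which is small and conservative. In a separate simulation of that omission alone (R² 0.02 to 0.10), the two models disagreed on p < 0.05 in about 0.5% to 1.0% of null trials and 1.1% to 4.8% of trials with an effect of 0.5 to 0.72 residual SD.

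Much of this stands. Section 7.9.2.2 is probably the intended model, the variance-ratio figures apply only to one reading, and the stale cross-reference is peripheral. But the behavioral section is the more specific text and lies closer to the pointers. It presents a list that reads as complete, whereas the fMRI subsection restates no model. It can therefore reasonably be taken as an override. Even on the most generous reading of the random effect, the two texts still disagree on the stratification factor.

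**Conclusion.** The point holds: the SAP is wrong as written, because it specifies two models where it promises one. The BMI omission is certain from the text. Its effect is modest and conservative: SE multiplied by 1.01 to 1.05 and type I error of 4.8% to 3.9%, for an assumed R² of 0.02 to 0.10. The effect of the random effect is conditional on how it is coded, and its direction is unknown. Over assumed SD ratios of 0.8 to 1.5, the SE multiplier runs from 0.91 to 1.28. The two models agree if BMI is not prognostic and the two visits have equal variance. At least 11 secondary analyses are exposed. The primary ANCOVA and the sample size are not affected.

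**What to change.** - Replace the independent-variable list under Behavioral Appetite Assessments with a reference, by number and title, to the MMRM in Section 7.9.2.2 (Secondary Pharmacodynamic Analyses): treatment, BMI stratum, week, treatment-by-week, baseline value, unstructured covariance, REML. Delete the patient random effect.
- Point the VAS, FCI, FCQ-S, TFEQ, Power of Food and BIS subsections to that section. For clarity, do the same in Section 7.9.2.3 (exploratory analyses) and Section 7.10.8 (body weight and waist circumference).
- State the unstructured matrix without the open qualifier, or say what replaces it. If a fallback for non-convergence is wanted, an ANCOVA at each week in the form of the primary model would serve. In the simulation, a Week 3 ANCOVA with BMI stratum gave the same SE as Section 7.9.2.2 (ratio 1.00 in every scenario, complete data).

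The cost is SAP wording only, provided it is done before unblinding. No data or subjects are added, and the two degrees of freedom for the three-level stratum are already in the Section 7.9.2.2 model.
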